4.1 Safety

Safety will be assessed by collecting adverse event data during the endovascular procedure, at 24 hours, 7 days or discharge (whichever occurs sooner), as well as at the 30-day and 90-day follow up.

4.2 Effectiveness

The effectiveness of the Penumbra Separator 3D will be assessed by the ability of the system to achieve TICI 2 or 3 flow in the target vessel at the site of the target occlusion. TIMI/TICI flow are classified in **Tables 8 A&B**.

Table 8A – Thrombolysis in Myocardial Infarction (TIMI) Flow Classification*

TIMI Score	Classification of Blood Flow
TIMI 0	No Perfusion
TIMI 1	Penetration without perfusion. Penetration past the initial occlusion, but no distal branch filling
TIMI 2	Partial perfusion of the artery with incomplete or slow distal branch filling
TIMI 3	Complete perfusion of the artery

* From Chesebro et al. *Circulation* 1987;76:142-154 and Khatri et al. *Stroke* 2005;36:2400-2403

Table 8B- Modified Thrombolysis in Cerebral Infarction (TICI) Perfusion Categories**

Grade 0:	No Perfusion. No antegrade flow beyond the point of occlusion.
Grade 1:	Penetration With Minimal Perfusion. The contrast material passes beyond the area of obstruction but fails to opacify the entire cerebral bed distal to the obstruction for the duration of the angiographic run.
Grade 2:	Partial Perfusion. The contrast material passes beyond the obstruction and opacifies the arterial bed distal to the obstruction. However, the rate of entry of contrast into the vessel distal to the obstruction and/or its rate of clearance from the distal bed are perceptibly slower than its entry into and/or clearance from comparable areas not perfused by the previously occluded vessel, e.g., the opposite cerebral artery or the arterial bed proximal to the obstruction.
Grade 2a:	Partial filling with <50% of the entire vascular territory is visualized.
Grade 2b:	Partial filling with ≥50% of the entire vascular territory is visualized. If complete filling of all of the expected vascular territory is visualized, the filling is slower than normal.
Grade 3:	Complete Perfusion. Antegrade flow into the bed distal to the obstruction occurs as promptly as into the obstruction and clearance of contrast material from the involved bed is as rapid as from an uninvolved other bed of the same vessel or the opposite cerebral artery.

** From Higashida et al. *Stroke* 2003;34:e109-37 and Tomsick et al. *AJNR* 2008;29:582-587

The investigator shall make an initial assessment of TIMI/TICI flow in the target

vessel. Pre-procedure and post-procedure angiograms shall be sent to an unbiased core laboratory blinded to treatment allocation to make a final determination on TIMI/TICI flow. A core laboratory with experience in performing intracranial angiographic analysis will be used.

4.3 Risk/Benefit Analysis

The risks associated with the Penumbra System and the Penumbra Separator 3D are similar to those associated with cerebral angiography and with other intra-arterial methods of revascularization.

4.3.1 Angiography

An angiographic procedure requires that a catheter be placed into the body, and in this case, threaded through the body to the neurovasculature. Once the catheter is in the proper position, contrast media is infused through the catheter to examine the vessels. Patients may encounter bleeding from vessel perforation, vessel spasm, swelling, or bruising at the access site where the catheters are placed in the body (usually the groin area). Additionally, once the catheter reaches the neurovasculature, there is a chance that the catheter could cause bleeding, hematoma, vessel thrombosis, dissection, distal embolization, psuedoaneurysm, and arteriovenous fistula formation. Patients who are allergic to contrast media are at further risk and may experience a reaction that may include hives, itching, nausea, or breathing difficulty. Contrast media may also cause kidney damage in some patients. The above risks of angiography are well known and generally unlikely to occur. However, if any of the above risks occur and are severe enough, patient death is possible.

4.3.2 Computed Tomography Scan (CT Scan)

The risks encountered during a CT scan are low. The risks mentioned above for contrast media allergy are possible with a CT scan. There is also a slight risk of injury from being exposed to the radiation associated with a CT scan; however, the levels of radiation, and the risks associated with radiation exposure are low.

4.3.3 Thrombectomy/Embolectomy

The risks of intra-arterial thrombectomy/embolectomy are similar to those associated with existing intra-arterial methods of recanalization. These risks include:

- allergic reaction and anaphylaxis from contrast media
- acute occlusion
- air embolism
- arteriovenous fistula
- death
- hematoma or hemorrhage at access site
- inability to completely remove thrombus
- infection
- intracranial hemorrhage
- ischemia
- kidney damage from contrast media

- device malfunction
- distal embolization
- emboli
- false aneurysm formation
- neurological deficits including stroke
- vessel spasm, thrombosis, dissection, or perforation

Risks directly associated with the Penumbra System and Penumbra Separator 3D are similar to the above. Considerable testing has been completed to ensure that the System does not pose a significant risk. Testing includes both *in vitro* and *in vivo* testing. In addition, the following will be performed to minimize the risks:

- Patients will be carefully evaluated before entering the study to ensure that the location of the occlusion and the time of stroke onset are appropriate for treatment with the Penumbra System.
- During the clinical study, the procedure will be performed in an Operating Room or in an angiographic suite with an Operating Room standby. Therefore, should complications arise requiring surgery or other interventions, the surgery or intervention can be initiated without delay. All sites will be carefully selected to ensure that either a stroke unit operating according to national stroke guidelines or a physician experienced in treating patients presenting with acute ischemic stroke is available.
- Patients will be carefully monitored during the study and the follow-up period. The Investigator will examine and perform various diagnostic tests before, during, and after the procedure, at 7 days or at hospital discharge, and at 30 days (± 10 days) and 90 days (± 10 days) after the procedure.
- In addition to monitoring data directly related to the Penumbra System, blood data will be obtained pre-operatively. This data will be used to determine the patients' coagulation status, to assess for infection as indicated by white blood cell count, and to detect significant internal bleeding with hemoglobin and hematocrit levels.
- Penumbra or its representatives will conduct site initiation visits at each investigational site before the study begins and periodically after patients have been enrolled. The first monitoring visit will be conducted at each site after inclusion of the first patients at each site in order to ensure that all aspects of the protocol are followed as well as to accurately record results, report adverse events, and keep records.

Use of the Penumbra System offers several potential benefits, which may include a higher success rate of recanalization with an acceptable device-related serious adverse rate.

Based on the above information, the benefits of the Penumbra System outweigh the potential risks associated with its clinical use.

5. Investigator Responsibilities

5.1 Institutional Review Board / Ethics Committee Approval

Prior to enrolling patients into the study, the investigator will ensure that proper Institutional Review Board (IRB)/Ethics Committee (EC) approval is obtained. The IRB/EC shall approve all study documents as appropriate, including the final protocol, amendments to the protocol, investigator brochure (where required), and the informed consent.

5.2 Informed Consent

The investigator is responsible for ensuring that the investigation is conducted according to this protocol and that a signed informed consent is obtained according to national and state requirements prior to inclusion of patients in the study.

5.3 Adverse Event Reporting

All adverse events or adverse device effects must be recorded by the investigator on the CRFs and must be carefully monitored during the entire study.

An ***Adverse Event*** is any undesirable clinical event occurring in a patient during a clinical trial, whether or not it is considered related to the investigational product. This includes a change in a patient's condition or laboratory results that has or could have a deleterious effect on the patient's health or well-being.

An ***Adverse Device Effect*** is any adverse event related to the investigational device.

A ***Serious Adverse Event***, a ***Serious Adverse Device Effect*** is an event that:

- a) Led to death
- b) Led to a serious deterioration in the health of the patient that:
 - Resulted in life-threatening illness or injury
 - Resulted in permanent impairment of a body structure or a body function
 - Required in-patient hospitalization or prolongation of existing hospitalization
 - Resulted in medical or surgical intervention to arrest permanent impairment to body structure or a body function
 - Led to fetal distress, fetal death or a congenital abnormality or birth defect

An ***Unanticipated Adverse Device Event*** is an event that has an ***Adverse Device Effect***, the specificity or severity of which is not consistent with the current investigator brochure; or, if an investigator brochure is not required or available, the specificity or severity of which is not consistent with the risk information described in the *Instruction for Use* or the clinical protocol.

Minimum requirements of data to be recorded are: type of event, duration of adverse event or adverse device effects (start through end), severity, seriousness, action taken, outcome and, if appropriate, causality.

The Investigator will report any serious adverse event or adverse device effect to the Sponsor or its designee as soon as possible, but no later than 24 hours after the event occurred. All serious adverse events or serious device effects must be documented on the Serious Adverse Events form along with an explanation of any medical treatment administered. The form must be completed, signed, and sent by fax or overnight courier to the Sponsor or its designee within five working days. This report must be followed by full written documentation.

An adverse event need not be reported as a serious adverse event if it represents only a relapse or an expected change or progression of the condition that was the cause of treatment without any symptoms and signs other than those present before procedure. This type of event only needs to be reported as an adverse event. The competent IRB/EC must be informed by the investigator about serious adverse events or device effects associated with the use of the product.

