3.4 Blinding

The Penumbra Inc. clinical team responsible for the conduct of the study, the investigator, and center study personnel will not be blinded to each patient's randomized treatment group throughout the course of the study. The study subjects and the Core Laboratory will be blinded to treatment assignment.

4 Interim Analysis

No interim analyses are planned for the purpose of stopping the study early.

5 Analysis Populations

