13.1 Clinical Events Committee/Data Safety Monitoring Board (CEC/DSMB)

A CEC/DSMB will adjudicate serious adverse events for causality and attribution.

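### Protocol 5.3 exempts relapse and progression from SAE reporting without an explicit exception for serious or possibly related events, so a re-occlusion that restores the original deficit can drop out of the primary safety endpoint

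*Protocol*

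**What the plan says.** **SAE definition (Protocol 5.3).** Seriousness is set by outcome. Death comes first, followed by life-threatening illness, permanent impairment, "Required in-patient hospitalization or prolongation of existing hospitalization", and intervention to prevent permanent impairment. The definition carries no exception.

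**Exemption (later in Protocol 5.3).** "An adverse event need not be reported as a serious adverse event if it represents only a relapse or an expected change or progression". What is meant is the condition being treated. The sentence has a limit: the event must be "without any symptoms and signs other than those present before procedure". It is followed by "This type of event only needs to be reported as an adverse event". The minimum data recorded for adverse events and device effects include "severity, seriousness, action taken, outcome and, if appropriate, causality".

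**Endpoint (Protocol 9.4.1, SAP 10.1).** The primary safety endpoint is the proportion of patients with a device- or procedure-related SAE in the first 24 hours.

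**Committee.** SAP 13.1 says "A CEC/DSMB will adjudicate serious adverse events for causality and attribution", and the synopsis agrees. Protocol 9.5 instead speaks of adjudicating the causality of adverse events generally. It also says that committee data override investigator data in AE analyses and refers to a charter.

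**Blinding (SAP 3.4).** "the investigator, and center study personnel will not be blinded to each patient's randomized treatment group".

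**Known risks (Protocol 4.3.3).** The listed thrombectomy risks include "acute occlusion", ischemia and neurological deficit.

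**The concern.** The exemption is limited by the type of sign, not by seriousness or relatedness. Its reference point is the state before the procedure, when every eligible patient already has an NIHSS of at least 8. A patient who improves and then falls back to the original deficit therefore shows nothing that was absent before the procedure, however serious the consequence.

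This matters because the treated disease and one known harm of the treatment can look the same at the bedside. Occlusion of the vessel is both the reason for the procedure and a listed risk of it. Whether such an event is progression of the index stroke or a complication is the attribution question that the committee is there to answer. The exemption lets a person who knows the arm answer it first, and that answer decides whether the event is labelled an SAE at all. At stake is the completeness of a primary endpoint and, if the label is applied differently by arm, the fairness of its comparison.

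**Working it through.** **1. One case, both rules.** Take a patient who enters with hemiplegia, reaches TICI 2 or 3, re-occludes at 6 hours (an illustrative time) with the same hemiplegia, and stays longer in hospital.

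| Question | Answer from the text |
|---|---|
| SAE by definition (Protocol 5.3)? | Yes, the stay is prolonged |
| Exempt (Protocol 5.3)? | It can be: a relapse with no sign beyond the pre-procedure ones |
| Which rule prevails? | Not stated |
| Could it be device- or procedure-related? | Yes, occlusion is a listed risk (Protocol 4.3.3) |
| Counted in the primary safety endpoint? | Yes if filed as an SAE, no if filed as an AE |

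**2. Does another primary endpoint catch it?** No. TICI is scored immediately after the procedure (Protocol 2.2.1), and Table 7 schedules no later angiography.

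**3. Does the committee restore it?** Under the synopsis and SAP 13.1 it receives SAEs only. Under Protocol 9.5 it may see the AE and judge its causality. Neither document gives it a decision on seriousness. An AE judged related is still not an SAE.

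**4. Size.** The plan gives no expected rate for this endpoint, so there is no safety figure to reproduce. The denominators come from the effectiveness calculation, which does reproduce: (1.645 + 1.036)² × 2(0.8)(0.2)/0.15² = 102.2, so 103 per group; 103/0.9 = 114.4, so 115.

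- One event: 1/115 = 0.87 percentage points, or 1/103 = 0.97 with the unadjusted number.
- Proxy rate: Protocol 1 gives 3.2% serious procedural complications in the single-arm pivotal study. 0.032 × 115 = 3.7 events per arm, and one event is 0.87/3.2 = 27% of that rate. It is only a proxy, because it refers to patients recanalized with the device and is not this endpoint.

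**5. Illustration of sensitivity (assumed rates).** Exact power of the two-sided Fisher test at 0.05 with 115 per arm, if a share of the true excess in the 3D arm is filed as ordinary AEs:

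| Control vs 3D, true rates | None exempted | 25% of excess | 50% of excess |
|---|---|---|---|
| 3.2% vs 13.2% | 0.74 | 0.51 | 0.26 |
| 10% vs 20% | 0.50 | 0.31 | 0.15 |

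In the first row the observed 3D rates are 13.2%, 10.7% and 8.2%. The table assumes that filtering touches only the excess in the 3D arm and that every exempted event would have been adjudicated as related. It shows how the test responds to lost events. It does not estimate how many are lost.

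**The case against.** The strongest reply is that the exemption is narrow and the event remains visible.

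- **It is limited.** Only events that are purely relapse or progression with no new sign qualify. New deficits and hemorrhage do not. A reader might infer that the exemption is open-ended; the text does not support that. This stands.
- **Fatal events.** A reader might infer that fatal events may be kept out. The documents do not say so. Death is the first SAE criterion, the decline before it would ordinarily bring new signs, and deaths to day 90 are counted whatever their SAE status (Protocol 9.4.2, SAP 10.5). What remains is the absence of an explicit exception for death, which is an ambiguity and not a permission.
- **Device effects are still reported.** Protocol 5.3 requires adverse device effects to reach the sponsor within 24 hours. This stands for events the investigator judges device-related. It does not put them in the SAE count, and it does not cover events judged related only to the procedure.
- **A related event is not purely progression.** This is true in principle, so only misattributed events are at stake. But the investigator makes that attribution before the committee does.
- **Committee data override.** Protocol 9.5 is not worded as confined to causality, and the charter is not among the documents, so it may say more. Neither the protocol nor the SAP mentions seriousness. A reader might infer that events escape a committee review of seriousness; no such review is described.
- **Other safeguards.** Seriousness is a recorded AE field, and NIHSS and CT are scheduled at 24±12 hours for everyone. These help detection, but SAP 10.1 does not say that they feed the endpoint.
- **An exemption limited to non-serious events is empty.** Largely so: it would only confirm that non-serious progression stays an AE. That is still clearer than two rules with no order between them.

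**Conclusion.** The point holds as an unreconciled gap. Within Protocol 5.3, the outcome-based definition and the exemption can both apply to a re-occlusion within 24 hours that restores the original deficit and prolongs the stay. Filed as an AE by an unblinded investigator, it would not count in the primary safety endpoint, and no passage returns it to the count.

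The number of events affected is unknown. Each is worth about 0.9 points in an arm of 115, roughly a quarter of the 3.2% proxy rate. If 1% to 3% of patients had a qualifying event (an assumption), that would be 1 to 3 per arm (0.01 × 115 = 1.2; 0.03 × 115 = 3.5), and only if every one were both related and exempted. That is a worst case, not a forecast. A reader might also infer that filtering will differ by arm; knowledge of the arm makes this possible, but nothing in the documents shows that it will happen.

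SAP 2 rests study success on effectiveness alone, so the gap cannot change that verdict. It bears on the completeness of a named primary endpoint and is worth correcting because the correction is cheap. The conclusion assumes that the charter, which was not available, does not already give the committee authority over seriousness.

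**What to change.** 1. **Protocol 5.3:** state that the exemption does not apply to any event meeting one of the section's own seriousness criteria, death included. Such events are reported as SAEs, and the CEC/DSMB decides whether they are device-related, procedure-related or due to the index stroke. The criteria themselves need not change; there is no need to make every re-occlusion or worsening an SAE regardless of them.
2. **SAP 10.1:** state that the endpoint uses seriousness and causality as adjudicated by the CEC/DSMB.
3. **Synopsis, Protocol 9.5 and SAP 13.1:** give one consistent remit, saying whether the committee receives all AEs or SAEs only and that it rules on seriousness. If the charter already covers this, carry it into these sections.

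The cost is one sentence each in Protocol 5.3 and SAP 10.1, the alignment of three short passages, somewhat more SAE forms and adjudication packets, and a slightly less favourable reported SAE rate. Patient care is unaffected.

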5.4 Adherence to Protocol/Amendments

The investigator shall approve and adhere to this protocol and any amendments that arise during the course of the study. Any deviations to the protocol shall be discussed with Penumbra prior to implementation, where possible, and shall be documented on the appropriate case report form. The investigator shall permit the Penumbra System to be used only under his/her supervision.

It is the investigator's responsibility to ensure that the staff assisting with the study have the appropriate qualifications, are fully instructed on the study procedures, and will respect the confidentiality statement.

The investigator will report to the Sponsor or designee immediately if, for any reason, the approval to conduct the investigation is withdrawn by the IRB/EC or Competent Authority. The report will include a complete description of the reason(s) for which approval was withdrawn

5.5 Case Report Form Completion

The investigator and study staff shall complete the case report forms associated with this study. Patient numbers shall be used to identify individual patients in this study. The Case Report Forms (CRFs) should be a complete and accurate record of patient data collected during the study according to ISO 14155 and Good Clinical Practices (GCP) requirements. It is the investigator's responsibility to ensure the quality of the data collected and recorded.

5.6 Administration of Neurological Exams and Stroke Scales

The principal investigator at each investigative site is responsible for the administration of the neurological examinations and grading of patients on the stroke scales (i.e., NIHSS, mRS). In cases where a designee is needed, the investigator must ensure that the designee is trained and has the appropriate qualifications to perform these functions.

5.7 Device Inventory Requirements

The investigator shall maintain records pertaining to device inventory. These records shall include:

- The disposition of each device including patient number and device lot number
- The serial numbers for investigational devices

The investigator will ensure that, for the purpose of this investigation, only trained physicians who are co-investigators in this study will use the Penumbra System.

5.8 Reports

The investigator shall submit all reports in a timely manner.

5.9 Records Retention

The investigator shall maintain the records associated with this study for a period of at least two years after either the date on which the investigation is completed or the date that the records are no longer required for supporting a premarket approval/notification submission, whichever is later. These records include the following:

- Correspondence with the Sponsor or designee, the Medical Monitor, and other investigators
- Accountability records of receipt, use, and disposition of all investigational devices and other study materials, including the following information:
 - The type and quantity of the device, the dates of receipt, and the study tracking number
 - The names of all persons who received, used, or disposed of each device
 - The number of devices that have been returned to Penumbra, discarded, or otherwise disposed of, and the reason for such action
- Patient Records, including Informed Consent Forms, copies of all completed CRFs, and supporting documents (laboratory reports and reports of diagnostic tests, medical records, etc.)
- Current study protocol with dates and details of reasons for any deviations from the protocol that could affect the scientific quality of the study or the rights, safety, or welfare of the patients
- *Instructions for Use*
- Reports of any serious adverse event or serious device effects
- A copy of all approvals related to the clinical investigation
- The approved, blank, informed consent form and blank CRFs
- Certification that the investigational plan has been approved by the IRB/EC
- Signed Investigator Agreements and current signed and dated *curriculum vitae* of the Principal Investigator and all participating co-investigators

6. Sponsor Responsibilities

